**Primary Efficacy Hypothesis** 

The primary efficacy hypothesis will be a joint superiority/non-inferiority hypothesis.

The superiority hypothesis is that the *relative risk* of revision at 10 years post-surgery in

the group of patients randomized to the Triathlon CR Total Knee System using the X3

polyethylene relative to the group of patients randomized to the Triathlon CR Total Knee

System using N2Vac will be less than 1.0.

The non-inferiority hypothesis is that the *relative risk* of revision at 10 years post-surgery

in the X3 polyethylene group relative to the N2Vac group will be less than 1.2. In other

words, the X3 polyethylene group will demonstrate a relative increase in the 10-year

revision rate no greater than 20% compared to the N2Vac group.

Formally the superiority null and alternative hypotheses are:

 $H_{S,O}$ :  $\pi_{X3}/\pi_{N2Vac} \ge 1.0$ , and

 $H_{S,A}$ :  $\pi_{X3}/\pi_{N2Vac} < 1.0$ , where  $\pi_{X3}$  is the ten-year revision rate in the Triathlon CR

Total Knee System group using the X3 polyethylene and  $\pi_{N2Vac}$  is the ten-year

revision rate in the Triathlon CR Total Knee System group using the N2Vac.

The non-inferiority null and alternative hypotheses are:

 $H_{NI,O}$ :  $\pi_{X3}/\pi_{N2Vac} > 1.2$ , and

 $H_{NI,A}$ :  $\pi_{X3}/\pi_{N2Vac} \le 1.2$ , where  $\pi_{X3}$  and  $\pi_{N2Vac}$  are defined as above.

**Secondary Efficacy Hypothesis** 

For the secondary efficacy parameters (when data is available), a non-inferiority

hypothesis will be tested at each scheduled follow-up visit, similar to the primary efficacy

hypothesis.

In addition, a comparison of the scores at each post-surgery visit with baseline (i.e.,

improvement scores) will be tested to see if any improvement is seen for each parameter

and time point.

For categorical secondary parameters (i.e., radiographic success/failure, subsidence and

radiolucency), the non-inferiority alternative hypothesis is that the risk in the X3

polyethylene group is not  $\Delta_0$ % worse relative to the N2Vac treated group within the

period from surgery to the scheduled follow-up visit. Formally the non-inferiority null

and alternative hypotheses are:

 $H_{NI,O}$ :  $\pi_{X3}/\pi_{N2Vac} > \Delta_0$ , and

 $H_{NI,A}$ :  $\pi_{X3}/\pi_{N2Vac} < \Delta_0$ , where  $\pi_{X3}$  is the rate in the Triathlon CR Total Knee

System group using the X3 polyethylene,  $\pi_{N2Vac}$  is the rate in the Triathlon CR

Total Knee System group using the N2Vac, and  $\Delta_0$  is the equivalence limit

difference ( $\Delta_0$ ).

For continuous secondary parameters (i.e., ROM, KSS, SF12), the non-inferiority

alternative hypothesis is that the mean using the X3 polyethylene is not  $\Delta_0$  worse than the

mean using the N2Vac treated group within ten years. Formally the non-inferiority null

and alternative hypotheses are:

 $H_{NI,O}$ :  $\mu_{X3} \ge \mu_{N2Vac} + \Delta_0$ , and

 $H_{NI,A}$ :  $\mu_{X3} < \mu_{N2Vac} + \Delta_0$ , where  $\mu_{X3}$  is the mean in the Triathlon CR Total Knee System group using the X3 polyethylene,  $\mu_{N2Vac}$  is the mean in the Triathlon CR Total Knee System group using the N2Vac, and  $\Delta_0$  is the equivalence limit difference ( $\Delta_0$ )..

The equivalence limit differences are as follows.:

Parameter	Equivalence Limit Difference ( $\Delta_0$ )
Range of Motion (ROM)	10 degrees
KSS pain and motion	10%
SF-12	10%
Radiographic success/failure	No complete radiolucent lines
Subsidence and Radiolucency	No component subsidence

In addition, for the continuous parameters, a comparison of the scores at each postsurgery visit with baseline (i.e., improvement scores) will be tested to see if any improvement is seen for each parameter at each time point. That is, the formal hypothesis to be tested is that the difference is zero. This is tested by:

$$H_{I,O}$$
:  $\mu_{i,j} - \mu_{i,0} = 0$ , and

 $H_{I,A}$ :  $\mu_{i,j} - \mu_{i,0} \neq 0$ , where  $\mu_{i,j}$  is the parameter's true mean at nominal visit j for treatment group i, where i is either X3 or N2Vac, and  $\mu_{i,0}$  is the corresponding baseline parameter's true mean for treatment group i.

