### **Secondary Efficacy Parameters**

The secondary efficacy parameters include:

Active flexion, Passive flexion, Active extension, and Passive extension ROM at the 2, 5, 7 and 10-year visits.

KSS pain and motion scores at the 3 months, 2, 5, 7 and 10-year visit.

SF-12 scores at the 3 months, 2, 5, 7 and 10-year visit.

Radiographic success/failure at the 3 months, 2, 5, 7 and 10-year visits.

Radiographic failure is defined as a score of 10 or greater according to the Knee Society

Rotenographic Scoring System, regardless of symptoms. A migrating or shifting

prosthesis with or without the disappearance of radiolucent lines is also a failure

regardless of the score.

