# **Efficacy Analyses**

#### Methods

Primary Parameter: The relative risk of revision (X3 relative to N2Vac) at ten years will be computed and a 95% confidence interval on the rate ratio computed, assuming a Poisson distribution. If the upper end of the confidence interval for the rate ratio is less than 1.0, then the superiority hypothesis will be supported. Otherwise, if the upper end of the confidence interval is less than 1.2, then the non-inferiority hypothesis will be supported. Secondary Parameters: The categorical secondary efficacy parameters will be analyzed at each nominal visit by computing the 95% confidence interval for the rate ratio (relative risk) of the groups as above. The clinically significant difference ( $\Delta_0$ ) is as presented on page 13 above. The continuous secondary efficacy parameters will be analyzed at each nominal visit. The 95% confidence interval on the difference between the two groups will be computed using the means, t-distribution and appropriate standard deviation. The change from baseline will also be presented and their 95% confidence interval and p-value for the paired t-test using the baseline will be presented for each nominal visit and treatment group, along with the descriptive statistics.

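### The formal non-inferiority hypotheses for the continuous secondary parameters run in the wrong direction for any parameter where higher is better

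*Combined protocol and SAP*

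**What the plan says.** The Secondary Efficacy Hypothesis section covers all continuous secondary parameters with one pair of hypotheses. The verbal statement begins "For continuous secondary parameters (i.e., ROM, KSS, SF12), the non-inferiority" and continues "alternative hypothesis is that the mean using the X3 polyethylene is not"; it goes on to say, in effect, worse than N2Vac by Δ0. The formal null is "\mu_{X3} \ge \mu_{N2Vac} + \Delta_0" and the formal alternative is "\mu_{X3} < \mu_{N2Vac} + \Delta_0". The table of equivalence limits gives Δ0 as a positive number: 10 degrees for ROM, and 10% for KSS pain and motion and for SF-12.

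The ROM measures in Secondary Efficacy Parameters are "Active flexion, Passive flexion, Active extension, and Passive extension ROM at the 2, 5, 7 and 10-year visits". KSS and SF-12 are listed at five visits (3 months and 2, 5, 7 and 10 years). No section states whether a larger value is better or worse for any of these measures.

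On the analysis, the Methods text under Efficacy Analyses says: "The 95% confidence interval on the difference between the two groups will be computed using the means, t-distribution and appropriate standard deviation". It gives no order of subtraction and no decision rule against Δ0. The limit it names for non-inferiority belongs to the primary rate ratio: "if the upper end of the confidence interval is less than 1.2, then the non-inferiority hypothesis will be supported".

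**The concern.** The formal pair has the shape of the primary hypothesis, where a higher revision rate is worse and an upper bound is the right protection. Applied to a mean where higher is better, the same shape protects against X3 being too good and allows any shortfall. The words and the symbols then describe different tests, and the analysis text does not choose between them.

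At stake is the formal non-inferiority conclusion at each visit. An analyst who follows the symbols could label X3 non-inferior on flexion when it is worse by more than the margin, and would withhold that label when X3 is better by Δ0 or more. An analyst who follows the words would avoid both errors, but would be departing from the written hypotheses, possibly after seeing the data.

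The number of tests involved follows from the visit schedule:
- Flexion: 2 measures × 4 visits = 8 tests, affected if larger flexion is better.
- KSS and SF-12: at least 2 × 5 visits = 10 tests, affected if higher scores are better.
- Extension: 2 measures × 4 visits = 8 tests, direction undefined. If extension is recorded as a deficit, the written sign is right for it.

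**Working it through.** **Logic.** Let d = μ(X3) − μ(N2Vac), with Δ0 > 0 and larger values better.

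- The words require d > −Δ0.
- The formal alternative requires d < +Δ0.

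These are mirror images. The null and alternative are complementary and both carry +Δ0, so a character lost in the PDF does not explain the conflict. Reading Δ0 as −10 does not rescue it either: the alternative becomes d < −10, which asks X3 to be more than 10 degrees worse. Changing only the plus to a minus gives the same result, so the inequality must be reversed too.

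**Inputs for the size of the effect.** The plan gives no power or error rate for these parameters, so there is no figure of its own to reproduce.

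- n per arm: 286 × 0.9 = 257, repeated at the 260 in Sample Size Justification.
- Margin: 10 degrees (table of equivalence limits).
- Interval: two-sided 95%, t-distribution (Methods; Data Summary).
- SD of flexion: not in the documents; assumed 10, 15 or 20 degrees.

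**Formulas.** SE = SD × √(2/n), df = 2n − 2. At n = 257, df = 512 and t(0.975) = 1.965.

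- SD 10: SE = 10 × √(2/257) = 0.882, half-width 1.965 × 0.882 = 1.73.
- SD 15: SE = 1.323, half-width 2.60.
- SD 20: SE = 1.764, half-width 3.47.

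Rule as written: declare non-inferiority if the upper 95% limit of d is below +10. Rule matching the words: declare it if the lower 95% limit is above −10. Both probabilities come from the noncentral t-distribution.

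**Results, n = 257 per arm, SD 10 / 15 / 20.**

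| True d (degrees) | As written | Matching the words |
|---|---|---|
| −10 | 1.000 / 1.000 / 1.000 | 0.025 / 0.025 / 0.025 |
| −8 | 1.000 / 1.000 / 1.000 | 0.619 / 0.326 / 0.204 |
| −5 | 1.000 / 1.000 / 1.000 | 0.9999 / 0.965 / 0.807 |
| 0 | at least 0.9998 | at least 0.9998 |
| +12 | 0.00001 / 0.0003 / 0.0010 | 1.000 / 1.000 / 1.000 |

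At n = 260 the rule matching the words gives 0.624 / 0.329 / 0.206 at d = −8 and 0.9999 / 0.967 / 0.812 at d = −5. A simulation of 20,000 trials per setting at n = 257 agreed: at d = −10 it gave 1.000 as written and 0.023 to 0.026 under the words.

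**KSS and SF-12.** These were not computed, because the base of the 10% margin is not stated. For illustration, with an assumed mean of 50 to 90 on a 0–100 scale, 10% of the mean is 5 to 9 points, while 10% of the scale is 10 points.

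**The case against.** The strongest reply is that the intent is already written down. The sentence before the formulas is clear, Methods calls Δ0 the clinically significant difference, and both confidence limits will be reported. A competent statistician would see a large flexion deficit and would not certify it. Following the words is then following the plan, so it is too strong to say that the rule must be chosen after the data. This is fair as to likely conduct. It does not remove the conflict: the formal hypotheses are also the plan, and no decision rule settles which governs.

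Further points stand in part:

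- The two rules do not give opposite answers everywhere. They agree at no difference and nearly agree at 5 degrees worse with SD 10. They separate as the deficit approaches the margin, and earlier when the SD is larger. The documents give no reason to expect a 10-degree loss or a 12-degree gain between two inserts in one knee system.
- The sample size for ROM is uncertain. Patients who do not return may answer by phone or mail, so measured flexion may be available for fewer than 257 per arm. At an assumed 130 per arm, SD 20 and d = −5, SE = 20 × √(2/130) = 2.48 and the rule matching the words gives about 52% rather than 81%. This widens the gap, but it shows that the exact percentages are illustrative.
- Describing the secondary tests by "hypothesis will be tested at each scheduled follow-up visit, similar to the primary efficacy" hypothesis need not import the primary's upper limit; it may refer only to the type of hypothesis. The firm point is that no limit is named for continuous parameters. Borrowing the upper one would repeat the error.
- The base of the 10% margins is a separate gap. It belongs in the same edit because the restated test cannot be run on KSS or SF-12 without it.

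**Conclusion.** The concern holds, with high confidence. For higher-is-better continuous parameters, the formal hypotheses contradict the stated meaning, and the analysis section does not resolve the contradiction. The logical error does not depend on any assumed SD.

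For flexion at the 10-degree margin, the written rule accepts a true 10-degree deficit about 100% of the time where 2.5% is intended, and rejects a true 12-degree advantage at least 99.9% of the time. Those figures rest on an assumed SD of 10 to 20 degrees, 257 to 260 evaluable patients per arm, and larger flexion being better. There is no harm if the arms are truly equal.

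The extension to KSS and SF-12 is conditional on their scoring direction, and extension ROM on its coding. Only secondary parameters are touched; the revision hypothesis and the sample size are not. This should be fixed, but it does not threaten the trial's main conclusion.

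**What to change.** 1. In Secondary Efficacy Hypothesis, for each higher-is-better parameter, restate the pair as H0: μ(X3) ≤ μ(N2Vac) − Δ0 and HA: μ(X3) > μ(N2Vac) − Δ0.
2. In Methods under Efficacy Analyses, add one sentence: the difference is X3 minus N2Vac, and non-inferiority is concluded when the lower 95% limit is above −Δ0.
3. Add a direction column to the table of equivalence limits covering active and passive flexion, active and passive extension, KSS pain and motion, and SF-12. Keep the present sign, with the upper limit below +Δ0, only for an extension measure coded so that larger is worse.
4. State what the 10% margins for KSS and SF-12 are a percentage of.

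The cost is two formula lines, one decision sentence, one table column and one definition. Item 4 needs a decision on the margin as well as an edit. All are changes to text only, with no effect on patients, enrolment or data collection. They should be made and dated before unblinded data are analysed.

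### A single 10-degree limit covers flexion and extension, which makes the extension test very weak, and the 10% limit for KSS and SF-12 has no stated base under an additive hypothesis

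*Combined protocol and SAP*

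**What the plan says.** Secondary Efficacy Parameters lists four range-of-motion measures: "Active flexion, Passive flexion, Active extension, and Passive extension ROM at the 2, 5, 7 and 10-year visits". KSS and SF-12 scores are also secondary, at three months and 2, 5, 7 and 10 years.

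Secondary Efficacy Hypothesis puts all of these under one formal test: "For continuous secondary parameters (i.e., ROM, KSS, SF12), the non-inferiority" alternative is written as "\mu_{X3} < \mu_{N2Vac} + \Delta_0". The limits come from the table in the same section, introduced by "The equivalence limit differences are as follows". The motion row reads "Range of Motion (ROM) 10 degrees", with no split between flexion and extension. The KSS row reads "KSS pain and motion 10" followed by a percent sign, and the SF-12 row also gives 10%.

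Efficacy Analyses, Methods, points back to that table for what it calls "The clinically significant difference". For the continuous endpoints it says: "The 95% confidence interval on the difference between the two groups will be computed using the means, t-distribution and appropriate standard deviation".

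The documents give no base for the 10%, no conversion to points, no score range, no separate extension limit and no justification for any of these limits.

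**The concern.** A non-inferiority limit has to suit the scale of the measure and be in units that the test can use.

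- **Extension.** Flexion covers a wide arc, while extension is recorded close to zero. The same 10 degrees is a much larger allowance, relative to spread, for extension. Two extension measures at four visits give eight tests that could support a non-inferiority claim despite a marked loss.
- **KSS and SF-12.** The hypothesis adds the limit to a mean, and the interval is for a difference in means. The limit must therefore be a number of points. A percentage becomes points only when its base is named, and two analysts could reach different conclusions from the same data.
- **Direction.** The printed alternative is met when the X3 mean is low. Where a low value is the bad outcome, the test rewards the worse result.

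**Working it through.** **The plan's own figures.** The only sample-size calculation is for revision. The Schoenfeld formula with rate ratio 0.32, two-sided 0.05 and 80% power gives 4 × (1.96 + 0.842)² / (ln 0.32)² = 24.2, so 25 events, against the plan's 26. Then 26 / 0.05 = 520, or 260 per arm, and 520 × 1.10 = 572. These figures reproduce, but they do not use the secondary limits. I take 260 per arm from here as the evaluable number.

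**Inputs not in the documents (assumptions).** Extension SD 2 to 5 degrees; flexion SD 10 to 20 degrees; SF-12 SD 10; scores on 0-100. Methods does not spell out the decision rule for continuous endpoints, so I follow the primary rule: X3 passes if the worse end of the 95% interval is inside the limit.

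**1. The 10-degree limit.** Half-width = 1.96 × SD × √(2/260) = 0.1719 × SD. The largest observed X3 deficit that passes is 10 minus the half-width.

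| Measure | SD | Limit in SDs | Half-width | Largest passing deficit |
|---|---|---|---|---|
| Extension | 2 | 5.0 | 0.34 | 9.7 |
| Extension | 3 | 3.3 | 0.52 | 9.5 |
| Extension | 5 | 2.0 | 0.86 | 9.1 |
| Flexion | 10 | 1.0 | 1.72 | 8.3 |
| Flexion | 20 | 0.5 | 3.44 | 6.6 |

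With 200 per arm and SD 5 the half-width is 1.96 × 5 × √(2/200) = 0.98 and the extension figure is 9.0, so the result hardly depends on retention. If the arms are truly equal, 80% power for the extension test needs only 1 to 4 patients per arm at these SDs.

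**2. The 10% limit.**

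- 10% of the score range: 10 points.
- 10% of an N2Vac mean of 80 to 90: 8 to 9 points.
- 10% of an N2Vac mean of 30 to 50: 3 to 5 points.

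For SF-12 with SD 10, n per arm for 80% power is 2 × (1.96 + 0.842)² × 10² / limit². That is 175 at 3 points and 16 at 10 points.

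The base can change the conclusion. Suppose the N2Vac mean is 50 and X3 is observed 4 points lower, with SD 10. The half-width is 1.72, so the worse end of the interval is 5.72. X3 passes against 10 points (10% of the range) and fails against 5 points (10% of the mean).

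**3. The test that fits a relative limit.** If 10% of the N2Vac mean is intended, the limit is itself estimated. The matching contrast is mean(X3) − 0.9 × mean(N2Vac), with half-width 1.96 × SD × √(1.81/260). In the same example the contrast is 46 − 45 = 1, the half-width is 1.64 and the lower limit is −0.64, so X3 fails. The plan's interval on a plain difference is not this test.

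**4. Direction.** Take flexion with SD 15 and X3 truly 20 degrees worse. The standard error is 15 × √(2/260) = 1.316. Read literally, the printed rule declares non-inferiority with probability Φ((10 + 20)/1.316 − 1.96) = Φ(20.8), which is about 1. The flexion rows in step 1 therefore hold only for the prose meaning (not worse by more than the limit), not for the formula as printed.

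**The case against.** The documents give no mean, range or SD for extension, so the claim that 10 degrees is too wide rests on outside assumptions. This stands as a limit on the size of the finding. It does not remove the documented fact that one limit serves four measures on two different scales.

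A reader might infer that the extension test cannot fail, or that X3 would pass at every visit. That goes too far: under the same assumptions X3 fails once the observed loss exceeds about 9.1 to 9.7 degrees. The test is very weak, not empty.

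On the 10%, a fair reply is that 10% of the N2Vac mean is in score units and can be added to a mean. The section says that the secondary tests resemble the primary one, and the primary limit of 1.2 is explained as a 20% relative increase over N2Vac. The N2Vac mean is thus the natural reading. This part is closer to an unstated base than to an unusable limit, but the natural reading still does not match the planned interval. For a KSS mean near 90, the choice between mean and range moves the limit only from 9 to 10 points.

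A reader might also infer that the limit would be picked after the means are known. Nothing in the documents says so; the wording only leaves that possible. Nor do they offer any support for fixing the base as the pooled baseline mean.

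Finally, between-group differences with 95% confidence intervals are reported at each visit, so readers will see the effect whatever the limit. That softens the consequence, but the plan still commits to formal non-inferiority conclusions.

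**Conclusion.** The point holds for the secondary endpoints only; the primary endpoint and the sample size are untouched.

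- The plan applies one 10-degree limit to flexion and extension. With an assumed extension SD of 2 to 5 degrees and 260 per arm, an observed loss of about 9.1 to 9.7 degrees would still count as non-inferior.
- The 10% for KSS and SF-12 has no stated base. On an assumed 0-100 score it is about 3 to 10 points, enough to change a conclusion.
- The printed inequality is in the wrong direction for flexion, KSS and SF-12, where higher is better. This needs no assumption about spread.

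**What to change.** Change the limits table and the continuous hypothesis in Secondary Efficacy Hypothesis, and the matching sentences in Methods, before any between-group comparison.

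1. Keep 10 degrees for flexion. Add a separate, smaller limit for active and passive extension, recorded as a deficit so that larger is worse, with a value that the investigators justify. As an illustration only, 5 degrees would remain testable: at SD 5 the half-width is 0.86, so observed losses up to about 4.1 degrees would pass.
2. For KSS and SF-12, either state each limit in points, or keep 10% of the N2Vac mean and require the lower limit of the 95% interval for mean(X3) − 0.9 × mean(N2Vac) to exceed 0, in place of the fixed-limit difference.
3. Write the inequality by direction. For flexion, KSS scores and SF-12 the alternative is μ(X3) > μ(N2Vac) − Δ0. For extension recorded as a deficit, the printed form is right.
4. State the decision rule for the continuous endpoints in Methods.

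The cost is a documented change to prespecified limits and a coding rule for extension, with no new data and no more patients. Non-inferiority on extension becomes somewhat harder to claim.

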# **Statistical Methodology**

#### **Data Summary**

All data entry and analysis will be done by the Mayo Clinic Division of Biostatistics.

The following is a detailed proposal of statistical analyses planned for data collected during the study. In general, data will be summarized by treatment group and nominal study visit, where applicable.

For parameters represented by continuous variables (e.g., ROM), the summaries will consist of the mean, median, standard deviation, minimum, and maximum values. Both the actual values at each nominal visit and the improvement from baseline at each post-baseline visit for each treatment group and their difference will be presented with its 95% confidence intervals. The improvement from baseline will also present the corresponding paired t-test p-values.

For categorical variables (e.g., subsidence), the number of events, person-years of follow-up, and the corresponding event rates with 95% confidence intervals will be presented.

In addition, the rate ratios (relative risk) of the treatment groups along with 95% confidence intervals will be presented.

Descriptive statistics and statistical comparisons for important demographic, efficacy, and safety variables will be provided in tables. All data collected on the case report forms will be provided in data listings, which will be sorted by treatment group and patient number.

Documentation of statistical analyses will be provided in a statistical appendix. All statistical analyses will be completed using SAS®, version 9 or higher (SAS Institute Inc,

Cary, NC), and Splus, version 7 or higher (Insightful Corporation, Seattle, WA).

All statistical tests will be two-sided and p-values less than 0.05 will be considered

significant.

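### The radiographic non-inferiority tests have no usable margin: the limit table gives descriptions of a radiograph where a number on the rate-ratio scale is needed

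*Combined protocol and SAP*

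**What the plan says.** The Secondary Efficacy Hypothesis section calls for a non-inferiority test at each scheduled follow-up visit. For the categorical outcomes (radiographic success/failure, subsidence and radiolucency) the null is π_X3/π_N2Vac > Δ₀ and the alternative is π_X3/π_N2Vac < Δ₀. The sentence introducing the formula expresses Δ₀ as the percentage by which X3 may be "worse relative to the N2Vac treated group within the" period up to the visit.

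The table of limits in that section has five rows:

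| Outcome | Δ₀ entered |
|---|---|
| Range of motion | 10 degrees |
| KSS pain and motion | 10% |
| SF-12 | 10% |
| Radiographic success/failure | "No complete radiolucent lines" |
| Subsidence and radiolucency | "No component subsidence" |

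Under Efficacy Analyses, Methods, the categorical outcomes are to be analysed by "computing the 95% confidence interval for the rate ratio (relative risk) of the groups as above", and Δ₀ "is as presented on page 13 above". No value is given there. The Primary Efficacy Hypothesis section states its revision margin in two matching forms: a relative risk of 1.2, and a relative increase in the "revision rate no greater than 20% compared to the N2Vac group".

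**The concern.** A non-inferiority test on a ratio needs a number to compare with the upper confidence limit. Two of the five rows have none, and those two rows cover every categorical secondary outcome. Radiographic success/failure alone is scheduled at five visits (3 months and 2, 5, 7 and 10 years, under Secondary Efficacy Parameters). Subsidence and radiolucency add further tests where data are available.

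The plan does not say that a margin will be set later. But if a non-inferiority statement is made at all, someone must supply the missing number, and if that happens after the interval is known, the choice can decide the result. The Introduction names wear debris and osteolysis as the limit on implant survival, and the Purpose section provides for independent radiograph review at 7 and 10 years. A radiographic non-inferiority claim would therefore carry weight with readers.

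**Working it through.** **1. Is there a number anywhere?** The formula needs Δ₀ on the ratio scale. The table gives text, the Methods paragraph refers back without a value, and the only ratio margin in the document (1.2) is attached to ten-year revision. The Sample Size Justification concerns revision only. Its figures reproduce closely: 4 × (1.96 + 0.8416)² / ln(0.32)² = 24.2, so 25 events against the stated 26; 26/0.05 = 520; 520 × 1.10 = 572. They supply nothing for the radiographs.

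**2. Would inserting a number be enough?** Not without fixing the scale.

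| Hypothetical entry | Ratio limit by the words (1 + Δ₀/100) | Ratio limit by the formula (Δ₀) |
|---|---|---|
| 20 | 1.20 | 20 |
| 1.2 | 1.012 | 1.2 |

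**3. How much depends on the missing number?** The document gives no radiographic event rate, so the counts here are assumed: *d* events in each arm, equal follow-up, observed ratio 1.0. The plan's own method is Poisson; the other two rows show that the method does not change the message. The binomial row uses 260 per arm, borrowed from the revision calculation.

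| Method | Upper 95% limit | At *d* = 25 |
|---|---|---|
| Poisson | exp(1.96 √(2/*d*)) | 1.74 |
| Exact conditional (Clopper-Pearson, 25 of 50, p/(1−p)) | – | 1.81 |
| Binomial, 260 per arm | exp(1.96 √(2/*d* − 2/260)) | 1.69 |

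By all three methods the same data pass a margin of 2.0 and fail 1.5 and 1.2. The fewest events per arm that pass at an observed ratio of 1.0 are:

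| Margin | Poisson | Exact | Binomial |
|---|---|---|---|
| 2.0 | 16 | 19 | 16 |
| 1.5 | 47 | 52 | 40 |
| 1.2 | 232 | 243 | 123 |

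**4. Power.** With an assumed 260 per arm, a 10% event rate in both arms (26 events each) and a true ratio of 1, Poisson power is Φ(ln *m* / √(2/26) − 1.96). This gives about 10% at *m* = 1.2, 31% at 1.5 and 71% at 2.0.

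**5. Total events for 80% power at a true ratio of 1.**
- Poisson: 4 × (1.96 + 0.8416)² / (ln *m*)² = 65.3 at 2.0 and 191.0 at 1.5.
- Binomial with 260 per arm: 2 / [(ln *m*)² / (2 × (1.96 + 0.8416)²) + 1/260] = 58.1 at 2.0 and 139.7 at 1.5.
- As shares of 520 patients: 11.2% to 12.6% at 2.0, and 26.9% to 36.7% at 1.5.

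**The case against.** The best defence is that the secondary hypotheses are introduced as resembling the primary one, which might be taken to import 1.2. That fails: the same section defines its own Δ₀ with its own table, and the Methods paragraph refers back for Δ₀ rather than to the revision margin.

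A second defence is that the phrases were meant as criteria for success. That is plausible, but they would still not be margins. The first would also have to be squared with the failure definition under Secondary Efficacy Parameters, which rests on a Knee Society score of at least 10 or on migration. Text extraction does not explain the entries either: each row has one entry, nothing suggests redaction, and even if the two were swapped, neither is a number.

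Several points on weight do stand:
- The outcomes are secondary, and the Data Summary section still ensures that "the rate ratios (relative risk) of the treatment groups along with 95% confidence intervals will be presented". What is lost is a yes/no conclusion.
- The 260 per arm is an assumption for radiographs. Study Procedures lets patients who do not return answer questionnaires by phone or mail, so some may have no film. With an assumed 200 radiographed per arm, the event shares in step 5 rise to about 14–16% at 2.0 and 32–48% at 1.5.
- The counts for a margin of 1.2 are illustrative only; 232 of 260 would mean 89% of patients with the event.
- The mismatch between words and formula would be settled as soon as a number is stated in both forms.

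**Conclusion.** The concern holds. The plan sets a formal test for the radiographic outcomes and gives a threshold of the wrong kind, so the decision cannot be carried out as written. This is an error in what is stated, not merely missing detail, and the percentage wording conflicts with the ratio formula as well.

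It affects two of five margin rows, including a test scheduled at five visits. Across margins of 1.2 to 2.0, the conclusion from identical data can reverse. That statement rests on assumed event counts and an observed ratio of 1.0; the absence of a usable margin rests on no assumption. The primary revision hypothesis, its 1.2 margin and the descriptive rate ratios are untouched. The plan should be corrected, but the point does not threaten the trial's main result.

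**What to change.** Before any unblinded radiographic comparison, remove the two phrases from the Δ₀ column and take one of two routes; the choice is the sponsor's.

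1. **Report without a decision.** State that radiographic success/failure, subsidence and radiolucency will be presented as rate ratios with 95% confidence intervals, and that no non-inferiority conclusion will be drawn.
2. **Keep the test.** Pre-specify a numeric ratio margin for each outcome with its own justification, written both as a percentage and as a ratio in the way the revision margin is. Do not carry 1.2 over from revision without justifying it for radiographs.

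Under either route, if the phrases were intended as event criteria, move them to the outcome definitions and reconcile the radiolucent-line criterion with the score-based failure definition.

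The cost is wording only, with no new data or patients. Route 1 gives up a formal claim. Route 2 keeps a claim that is hard to meet with few events: about 59 to 66 events in total for 80% power at a margin of 2.0, and about 140 to 191 at 1.5, on the assumptions above. This change concerns the categorical radiographic tests only and does not endorse the range-of-motion, KSS and SF-12 non-inferiority tests as written.
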